6.1 Study design

This study will compare PFS amongst 134 overweight women (BMI \geq 24 kg/m²) commencing chemotherapy who are randomised to:

1. Intervention group: Advised to follow an intermittent energy restricted diet and undertake resistance exercise.

2. Control group: Advised to undertake resistance exercise only (and to follow their normal diet).

6.2 Eligibility

- Inclusion criteria:
 - Women with histologically confirmed breast cancer
 - Patients with ABC, i.e. locally advanced disease that is not amenable to curative surgical resection or with metastatic disease
 - HER2 positive or negative
 - ER and/or PR positive or negative
 - If ER positive there is no restriction on the number of lines of previous endocrine therapy for ABC
 - Performance status 0 or 1
 - Predicted life expectancy \geq 3 months
 - BMI≥24 kg/m²
 - Expressing a wish to lose weight
 - Not already entered or planned to enter a trial of an investigational medicinal product (IMP) for this line of therapy
 - Age >18 (can be pre or post menopausal)
 - Measurable or non-measurable disease by RECIST v1.1
 - Patients with brain or leptomeningeal metastases are eligible as long as all sites have been treated with radiotherapy (+/- surgery) with evidence of disease control at least 8 weeks after the last dose
 - Women in whom further endocrine therapy is planned after chemotherapy are eligible. The treating clinician must state what endocrine therapy is planned before chemotherapy is initiated.
 - Women with thyroid dysfunction are eligible provided they are euthyroid and on a stable dose of thyroxine for the last 6 months
- Exclusion criteria:
 - Physical or psychiatric conditions which may reduce compliance to and the safety of diet or resistance exercise, e.g.
 - Serious digestive and/or absorptive problems, including active inflammatory bowel disease.
 - Psychiatric disorders or conditions, e.g. history of eating disorders, untreated major depression, psychosis, substance abuse, severe personality disorder.

- Bone metastases at risk of pathological fracture or that would limit resistance exercise through pain in all three areas of the body that are covered by the resistance exercises (upper limbs, trunk and lower limbs). Metastases may be ok if other areas of the body can safely be exercised.
- Medications affecting adiposity or muscle mass and function and energy intake e.g. continuous daily steroids for longer than 4 weeks (short term steroids with chemotherapy are acceptable)
- Diabetics on insulin or sulphonylureas (glibenclamide, gliclazide, glimepiride, glipizide, tolbutamide) as they could experience hypoglycaemia on restricted days of the intermittent diet (diabetics treated with diet alone or with any other medication including metformin are eligible)
- Greater than Day 15 of this course of chemotherapy.
- Visceral metastases that, in the opinion of the treating clinician, would result in death within 3 months if no response was achieved with this line of chemotherapy
- Symptomatic or uncontrolled brain or leptomeningeal metastases

6.3 Recruitment

Patients due to commence chemotherapy for advanced breast cancer will be invited to the study by their oncology team and National Cancer Research Network (NCRN) nurses in 11 Greater Manchester and Cheshire Cancer network breast units (Christie, Wigan, Macclesfield, Bolton, Tameside, North Manchester General Hospital, Oldham, Leighton, Stockport, Salford and Blackburn) at the start of the study and more sites in the UK will be added depending on recruitment.

All research nurses in participating centres will be fully informed about the study and recruitment procedure. Eligible patients will be identified by NCRN research nurses either at the metastatic breast cancer multidisciplinary team meeting or by screening clinic notes. Eligible women will be given a detailed patient information sheet and given the opportunity to ask questions concerning the trial. If it is not possible to see women in clinic, they will be telephoned by the research nurse or other member of the B-AHEAD 3 research team. The purpose of this phone call will be to briefly introduce the study and get consent to post or e-mail an information sheet to the participant if they are interested. We will seek permission for the research nurse or other member of the research team to contact them at least 24 hours after receipt of the information sheet to determine their interest in entering the trial. Ideally, interested women will be asked by the research nurse to reattend to sign a consent form. At that appointment they will also be asked whether they consent to their details being securely transferred on the trial proforma by fax or nhs.net e-mail to the B-AHEAD 3 research team at MFT. This verbal consent will be documented. If it is in the participant's interest, consent could be taken during the same visit to the recruiting centre. This would allow the participant to avoid an extra journey to hospital solely for consent (for example if they didn't have any other visits planned before chemotherapy started, or to allow a participant to take part in the study if they were interested but the time frame was tight and chemotherapy would potentially need to be delayed to allow them to reattend their local hospital/the Nightingale Centre for consent). Consent can also be attained at the baseline appointment at The Nightingale Centre, if the participant has given verbal consent for their details to be transferred to the study team at MFT.

Once the proforma has been received, the B-AHEAD 3 research team at MFT will then contact the patient to arrange a baseline appointment. The baseline appointment should ideally occur at least 2 days before commencing the planned course of chemotherapy. However potential participants will be informed that they can join the study at any time up to Day 15 of their chemotherapy cycle.

Using the initial approach we have successfully recruited 47 - 48% of eligible chemotherapy patients from the Greater Manchester NIHR Clinical Research Network into our previous randomised diet and

exercise B-AHEAD 1 and B-AHEAD 2 studies in the same hospitals outlined above. Assuming a conservative 35% uptake amongst advanced breast cancer patients we anticipate recruitment should be completed within 15 months.

Ideally baseline assessments will take place at The Nightingale Centre. It is recognised that between consent and undergoing the baseline assessments at The Nightingale Centre, participants have time to change their mind about joining the study so we are not concerned that not having this consent visit would make women join the study before they have had time to consider it.

As recruitment has been slower than anticipated, participants can now have their baseline assessments and blood samples in their recruiting hospital. Blood samples will only be taken if the centre has -80°C storage facilities or if the samples can be transferred to MFT or another centre with -80°C storage facilities within an acceptable time frame.

If baseline assessments are taking place at the recruiting hospital, there must be at least 24 hours between the participant receiving the PIS and the assessments taking place in order to allow the participant time to consider the study.

Posters and leaflets to raise awareness of the study will be displayed in patient areas.

6.4 **Procedures for during and end of the study**

The energy restriction and exercise interventions will continue until the first disease progression after commencement of study chemotherapy, even if chemotherapy had been stopped due to toxicity. Approximately 30% of patients have an objective response, whilst 20% have stable disease. The average chemotherapy period of treatment is projected to be 5.4 months. The longest treatment period is predicted to be two years. We plan to censor patients in the study once the final recruited patient has been in the trial for 12 months.

Chemotherapy toxicity will be managed according to standard protocols within the Christie NHS trust and the other hospitals. All patients will have access to the 24 hour Christie chemotherapy hot line or local hot line for advice as to the management of toxicity, as well as their breast care nurse and the research nurses.

As the *a priori* aim of the study is for participants on the diet arm to lose weight, a loss of greater than 10% body weight may be seen more frequently on the intervention arm than the control group. In this case, if grade ≥ 2 toxicity has been observed within the last 2 cycles before the weight loss reached 10% or more, a dose reduction should be performed by recalculating the body surface area with the most recent weight. If no grade ≥ 2 toxicity is observed then no dose recalculation should be performed. If therapy is continued in this a manner and grade ≥ 2 toxicity develops subsequently then the recalculation should be performed on the most recent weight, not the one first observed to be <10% from baseline.

A change of chemotherapy regimen is not permitted prior to disease progression. This includes a switch from paclitaxel to 'maintenance' capecitabine which is specifically prohibited. A patient who has an allergic reaction to the first or second dose of weekly paclitaxel, who has not been treated previously with capecitabine, may change to capecitabine if, in the opinion of the treating clinician, this is an appropriate therapeutic option. HER2 targeted agents may be stopped during the study and the patient continue with chemotherapy. The date of stopping the HER2 targeted agent will be recorded.

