7.3.3 Monitoring weight

All patients will have their weight monitored at each chemotherapy cycle in their chemotherapy unit. This will allow us to make any necessary modifications to their dietary prescription if patients are losing too much weight (see section 16.1 'Acting on low weight and BMI'). A change in weight by - 10% alongside a grade ≥ 2 toxicity (as per section 6.4) will be communicated to the patient's medical oncologist so they can consider whether they wish to adjust the chemotherapy dose, which are dosed according to body weight and body surface area (see section 6.4 'Procedures for during and end of the study'). Patients in Group 1 will be provided with a diary to record their weight and waist.

7.3.4 Monitoring after discontinuation of chemotherapy due to excess toxicity or at the end of planned treatment

Participants will be offered three options at this point as they will no longer be having visits to their chemotherapy hospital at each cycle:

- 1. Continue with B AHEAD 3 phone calls from the research dietitian/ physiotherapist and attend for study assessments at chemotherapy centre around every 8-12 weeks (these appointments will hopefully coincide with visits to the centre for CT scans or clinic appointments)
- Don't attend for any more study assessments with research nurses, but continue with phone calls from B-AHEAD 3 research dietitian/ physiotherapist until CT scans show tumour progression
- 3. Don't attend for any more study assessments with research nurses, no more phone calls from B-AHEAD 3 study team CT scans will continue to be monitored until tumour progression

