16.1 Acting on low weight and BMI

The study team will collect weight from participants at their three weekly phone calls. If a participant has not recorded this information or if the study team have concerns about the validity of this information they will contact the relevant hospital team in order to create an accurate and complete record. The study team will calculate percentage weight change and alert the participant's medical oncologist and chemotherapy nurse if weight loss or gain exceeds 10% as this may require a reassessment of chemotherapy dose. BMI will be calculated and study dietitians will give advice on increasing calories if BMI goes below 19 kg/m².

Patients on the intermittent diet who achieve their healthy weight aim during the trial and are trying to maintain their weight should be encouraged to include 2 restricted days each week, whilst increasing amounts of the healthy Mediterranean diet (i.e. carbohydrate, protein and fat allowances) on the other 5 days.

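### Sections 6.4, 7.3.3 and 16.1 give inconsistent instructions on chemotherapy dose after a 10% weight change, so sites could handle the same patient differently

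*Protocol*

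**What the plan says.** Three sections of the protocol deal with a 10% change in body weight during chemotherapy.

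- **Section 6.4** (procedures during and at the end of the study) first notes that "a loss of greater than 10% body weight may be seen more frequently on the intervention arm than the control group". It then sets a condition, "if grade ≥ 2 toxicity has been observed within the last 2 cycles before the weight loss reached 10% or more", and an action: "a dose reduction should be performed by recalculating the body surface area with the most recent weight". For the remaining patients it adds: "If no grade ≥ 2 toxicity is observed then no dose recalculation should be performed". If toxicity of that grade appears later, the recalculation is then to be made on the latest weight.
- **Section 7.3.3** (monitoring weight) has every patient weighed at the chemotherapy unit at each cycle. It uses the same trigger as 6.4, a 10% loss with grade 2 or worse toxicity, and refers to 6.4 twice. The action differs: the change "will be communicated to the patient's medical oncologist so they can consider whether they wish to adjust the chemotherapy dose".
- **Section 16.1** (acting on low weight and BMI) has the study team collect weight at the three-weekly calls, going to the hospital team when the information is missing or doubtful. The team alerts the oncologist and chemotherapy nurse "if weight loss or gain exceeds 10% as this may require a reassessment of chemotherapy dose". No toxicity condition is attached.

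**The concern.** A site following one section may act differently from a site following another. The disagreement concerns whether a dose change is required, optional or ruled out, so it is a patient-safety matter before it is a statistical one.

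The statistical side concerns interpretation. The aim in section 5 is that the diet improves efficacy and ameliorates the toxicity of chemotherapy, and toxicity is the first secondary objective in section 5.2. A dose cut prompted by toxicity can itself lower later toxicity. If such cuts fall more often on the diet arm, part of any toxicity advantage could come through a lower dose. With inconsistent text, a reader of the results could not tell which dose policy patients were under, or how much of a difference ran through dose.

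**Working it through.** The point is mainly textual. The protocol gives no figure for how many patients will lose 10%, or for the resulting change in dose, so there is no stated figure to reproduce. The sample size does not depend on this point.

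**Step 1: the sections side by side.**

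| Situation | Section 6.4 | Section 7.3.3 | Section 16.1 |
|---|---|---|---|
| Loss above 10%, recent grade 2 or worse toxicity | Reduction directed | Oncologist told; change optional | Alert; dose may need reassessment |
| Loss above 10%, no such toxicity | Recalculation ruled out | No communication triggered | Alert; dose may need reassessment |
| Gain above 10% | Not covered | Not covered | Alert; dose may need reassessment |

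Row 1 is a conflict between 6.4 and 7.3.3 over whether the action is required. Row 2 is a tension between 6.4 and 16.1: one rules recalculation out, and the other prompts the oncologist to think about it without mentioning that limit. Row 3 is not a contradiction, because only 16.1 speaks to gain, but it leaves the status of the alert open. The boundary also varies slightly: the 6.4 condition includes a loss of exactly 10%, while 16.1 requires more than 10%.

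**Step 2: size of one recalculation.** The protocol names no body-surface-area formula. Two common forms are assumed, with height fixed: area proportional to weight to the power 0.5 (Mosteller) or 0.425 (DuBois). For a fractional loss L, the relative fall in a dose based on body surface area is 1 − (1 − L)^k.

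- L = 10%: 1 − 0.90^0.5 = 5.1%; 1 − 0.90^0.425 = 4.4%.
- L = 15%: 7.8%; 6.7%.
- L = 20%: 10.6%; 9.0%.
- A 10% gain would raise the dose: 1.10^0.5 − 1 = 4.9%; 1.10^0.425 − 1 = 4.1%.

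**Step 3: size between arms.** Let d be the excess share of diet-arm patients whose dose is recalculated at 10% loss. The protocol does not give d, so 10% to 40% is assumed. The difference in mean dose is d times the fall from step 2.

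- Low end: 0.10 × 4.4% = 0.4%.
- High end: 0.40 × 5.1% = about 2.1%.

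These figures describe dose only. The protocol gives nothing from which to convert them into an effect on toxicity or progression-free survival.

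**The case against.** The best case for the protocol is that there is only one dosing rule, in 6.4. On that view 7.3.3 merely describes how the oncologist is told, since it cites 6.4 and shares its trigger. Section 16.1 sets an alert, and an alert may properly be wider than the rule it serves. Part of this stands: 16.1 directs no dose change, and no section directs one for every patient with a 10% change. It does not remove the conflict. Section 7.3.3 turns a directed action into an option while citing the section that directs it, and 16.1 does not say that its alert is subject to 6.4.

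Stronger readings are tempting but not supported.

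- **That the conflicting text confounds toxicity and progression-free survival.** All three sections apply to both arms. Any imbalance would come mainly from the diet causing more weight loss, and would persist under one consistent rule. Dosing after randomisation is a co-intervention that follows from allocation, not a confounder. The intention-to-treat comparison (section 9) remains valid for the strategy as a whole. Differences between sites mainly add noise, although site is not among the listed minimisation factors.
- **That the arms are weighed differently.** Only Group 1 receives a weight diary, and 16.1 relies on phone calls. But 7.3.3 has all patients weighed at the unit each cycle, 16.1 falls back on the hospital team, and nothing bases a dose on the diary.
- **That the protocol predicts an imbalance.** Section 6.4 says only that loss above 10% may be more frequent on the diet arm, and gives no frequency.
- **That dose received is already captured.** Section 15 lists treatment schedules as source data without saying that they record dose. Section 17 mentions only dates of cycles.

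**Conclusion.** The inconsistency is real and can be seen on the page. For loss with grade 2 or worse toxicity, 6.4 requires what 7.3.3 makes optional. For loss without it, 6.4 rules out what the 16.1 alert invites the oncologist to consider. Sites could handle the same patient differently, and that alone justifies correction on safety grounds.

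The statistical consequence is narrower: attribution of a toxicity difference to the diet, rather than partly to dose, is weakened. Each recalculation at 10% loss lowers a dose based on body surface area by about 4% to 5%. Mean dose would differ between arms by about 0.4% to 2.1% if an assumed 10% to 40% more diet-arm patients were recalculated. Both ranges rest on assumed formulas, and the second also on an assumed share. A large bias in progression-free survival is not shown, and the comparison of the two strategies as randomised is not invalidated.

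**What to change.** The sponsor's clinicians should reconcile sections 6.4, 7.3.3 and 16.1 into one instruction that:

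- states one trigger, including the exact threshold, whether toxicity is part of it, and whether weight gain is covered;
- states one status for the action, required or optional;
- says that the 16.1 alert is subject to that instruction;
- applies identically in both arms, using the chemotherapy-unit weight that 7.3.3 already has measured at each cycle in all patients.

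Which trigger and which status are clinically right is for the clinicians; this review takes no position.

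Separately, confirm that the treatment schedules in section 15 record the dose given. Then report dose recalculations and dose received by arm, beside the toxicity and progression-free survival results. This is worth doing even after the text is reconciled, because a single rule would not remove an imbalance that arises from weight loss on the diet arm.

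The cost is amendment wording, a letter to sites and one additional table. If dose is not recorded at present, a field on the case report form or retrieval from hospital prescribing records would be needed as well.

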7.1 Intervention group: Intermittent diet & resistance exercise

7.1.1 Intermittent energy restriction

Women will be asked to follow the intermittent diet for 2 days/week throughout the trial ideally beginning 2 days immediately prior to the first chemotherapy cycle or before the 2nd cycle if recruited within 2 weeks of starting chemo. The 2 restricted days must be consecutive and should be the 2 days immediately prior to the first dose of chemotherapy at each cycle. If this is not possible alternative days should be undertaken, as this is preferable to none or a reduced number of restricted days. The restricted days limit carbohydrate intake (<50 g per day) and has been found to be effective and successful in a non-cancer population as the diet is palatable and satiating. The two restricted days include generous amounts of lean meat, fish, eggs, tofu and monounsaturated fat (MUFA), five portions of vegetables and one portion of fruit, limited vegetarian protein foods and low fat dairy foods which contain some carbohydrate i.e. Quorn, hummus, and at least 2 litres of low energy fluids (43). The diet typically self-limits to 70–90 g protein and <60g fat/day and is limited in saturated (82) and PUFA fat (51), which have possible links with breast cancer. We will encourage a high fluid intake which is important as this population may suffer chemotherapy-induced constipation.

Women will be asked to follow a healthy Mediterranean type diet for the remaining five days of the week. Energy intake on these days will be tailored according to their estimated energy requirements to lose weight. The Mediterranean diet provides 30% energy from fat (15% MUFA, 8% PUFA, 7% saturated), 25% energy from protein and 45% from low glycaemic load carbohydrate and includes at least five portions of vegetables and two portions of fruit per day and is limited in alcohol (<10 units per week).

7.1.2 Home based resistance exercise programme

The programme has been designed by our specialist breast cancer physiotherapists ([name], [name]) adapted from Cormie et al (65). The resistance exercise programme includes three sessions per week. It includes a brief warm up, and 5-10 standard exercises for muscle groups in the lower limbs, upper limbs and trunk and a cool down. The trial physiotherapist will adapt this standard resistance programme for patients at baseline according to their metastatic site, co-morbidities and current activity and energy levels (Appendix 1). The programme is designed to be progressive with 3 progressive stages. The speed of progression will be advised according to feedback on function and energy levels from participants and will occur after 4 - 8 weeks. Progression will be achieved with the same type of exercises by increasing the number of reps and sets and increasing resistance when exercising by using simple home light weights (i.e. holding a 500 ml bottle of water = 500g).

Participants will be shown the correct technique for undertaking the resistance exercises via a face to face or telephone baseline appointment with the trial physiotherapist, including the correct speed to undertake the exercises. Some exercises may be advised to be undertaken when seated or lying down depending on the site of any bone metastasis. Women with lymphoedema will be asked to wear their sleeve when undertaking upper body exercise. Participants will be provided with demonstration on line videos and written leaflets of their recommended exercise programme to use at home using an on line physiotherapy tool (Physiotec, Canada www.physiotec.ca). Medical oncology teams will inform the B-AHEAD 3 team of any change in health status and metastases which may require adaptations to the programme as the trial progresses.

The trial is specifically testing the benefits of an energy restricted diet and resistance exercise programme, and is not testing the effects of cardiovascular exercise. Large increases in moderate (60-75% maximum heart rate) or vigorous (75–90% maximum heart rate) cardiovascular exercise in trial participants could be a confounder which could have a positive influence on weight loss and possibly outcome (83). We acknowledge that some patients may wish to undertake cardiovascular exercise. Patients will be given general guidance to include 150 minutes of moderate (not vigorous) activity per week as per standard health advice for cancer patients receiving chemotherapy and for general health (84). We do not however anticipate that large increases in moderate exercise are likely to be achieved by our trial participants. Previous attempts to increase cardiovascular exercise amongst metastatic cancer patients have only managed to promote modest increases in light (50 – 60% maximum heart rate), but not moderate cardiovascular exercise (62, 63). A recent home based walking programme only achieved an additional mean (95% CI) of 77 (1.9 to 152) minutes of low intensity walking at 1.7 mph (2.7 km/h) on level ground per week (65). Light exercise, e.g. low intensity walking, light housework, gardening has been associated with modest improvements in well-being and fatigue, and will be encouraged alongside the resistance exercise programme. We will assess the actual amount of moderate or vigorous cardiovascular and resistance exercises undertaken in the previous 7 days at baseline, cycle 3 and then every 3 cycles after that in the trial using the Scot-PAO questionnaire. This will be compared between the groups.

